Nutrition assessment surveys described herein will be carried out most often among displaced or emergency-affected populations. Such populations, if displaced, are sometimes settled in camps and sometimes integrated into the host community or both. Regardless of pattern of settlement, surveys will often select a sample of households and include in the survey sample all members of targeted groups who reside in those households on the day of data collection. Targeted groups may include children less than 5 years of age, women of childbearing age, school age children, adolescents, adult men, or other groups depending on the nutritional conditions to be assessed.

Case definitions

Case definitions for nutritional deficiencies commonly included in nutritional assessment surveys in emergency-affected populations are given below:

Protein-energy malnutrition in children less than 5 years of age: Undernutrition, including wasting, stunting, and underweight, in children less than 5 years of age is defined using the NCHS:CDC:WHO reference population of children. When it becomes available, the new World Health Organization (WHO) international reference population will be used instead. Children with z-scores below -2 for weight-for-height, height-for-age, or weight-for-age are defined as wasted, stunted, or underweight, respectively. Moderate wasting, stunting, and underweight are defined as a z-score less than -2 but greater than -3. Z-scores less than -3 define severe wasting, severe stunting, or severe underweight.

For children less than 5 years of age, mid-upper arm circumference (MUAC) is sometimes used to assess protein-energy malnutrition when measuring weight and height are not feasible. MUAC measurements less than 11.5 cm are classified as severely low. MUAC measurements of 11.5 - 12.4 cm are considered moderately low, and MUAC 12.5 cm or greater are considered normal.

Protein-energy malnutrition in adults: Malnutrition in adults is assessed using body mass index (BMI), which is calculated by dividing the weight in kilograms by the square of the standing height in meters. The most common cut-off points for BMI to define levels of malnutrition in nonpregnant adults are shown below.

BMI	Category of malnutrition
< 16.0	Severe
16.0 - 16.9	Moderate
17.0 - 18.4	At risk
18.5 - 24.9	Normal
25.0 - 29.9	Overweight
> 30	Obese

An alternate scheme uses both MUAC and BMI to determine the level of malnutrition according to the scheme shown below.

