Measles immunization coverage. Measles immunization status is most often determined by asking an adult caretaker, preferably the mother, if the child has ever been vaccinated against measles. In some populations where mothers have written health records, such as vaccination cards, evidence of measles vaccination will consist of a written record of immunization. In other populations where vaccination cards are not widely available, the mother's verbal report will serve as evidence of vaccination.

Cumulative prevalence of diarrhea and acute lower respiratory infection. During interviews with an adult caretaker, survey workers define diarrhea as 3 or more bowel movements in the prior 24 hours. The child's having had diarrhea at any time in the prior 2 weeks is considered positive. Acute lower respiratory infection is defined as the presence of cough and fever; having this condition at any time in the prior 2 weeks is considered positive.

Participant inclusion criteria

Households are eligible for participation in nutrition assessment surveys if they fit the clearly defined criteria established before sampling takes place. Such criteria are most often geographic because most surveys are done to estimate nutritional status in a geographically defined emergency-affected population or the population of a specific camp. Individuals in selected households are eligible for participation if: 1) they fit the criteria defining a target subgroup, such as children 6-59 months of age, women of child-bearing age, etc. 2) they live in a selected household at the time of data collection, and 3) consent is given by the participant or a responsible adult for survey participation.

Participant exclusion criteria

Households will be ineligible for participation in nutrition assessment surveys if 1) they are empty, that is, if no one from the household currently lives in the defined population, or 2) consent for participation is denied by the adult household member approached by the survey team. Individuals in selected households will be ineligible if consent is denied.

Justification of exclusion of any sub-segment of the population

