No. of HHs in		No. of HHs	No. of HHs in	No. of HHs in
sampling frame		in PSU	secondary unit	sampling frame

* PSU = Primary sampling unit (also called clusters)

30 = Number of clusters

 $^{\sim}20 =$ Number of households selected in each cluster

In order to carry out selection probability proportional to size, the list of sampling units must contain some indicator of the relative size of each sampling unit. The indicator of size for the sampling units in all but the final stage of sampling is ideally the number of basic sampling units (households in the Afghanistan example above). However, in some cases, another measure of size must be used. For example, if the final sampling stage chooses children 6-59 months of age, the number of children in each primary sampling unit should be the measure of size to achieve probability proportional to size. However, these data may not be available. In such a

case, a surrogate measure of the size of each primary sampling unit, such as total population or number of households, may have to be used to approximate probability proportional to size sampling. Such uses of such surrogate measures of size should not substantially bias the final estimates of prevalence or incidence.

Enrollment procedures

Upon presenting themselves to an adult in a selected household, survey team members will explain the survey purpose, methods, and procedures, and request verbal consent from this adult (see section below "Supplemental information for protection of human research participants" for more information on the consent process). All household members who fit the criteria for a target group will be included in the survey if consent is received. At the start of the survey team's visit to a selected household, household members or others in the community will be asked to fetch absent household members who are eligible for survey inclusion; however, the team will not be able to wait for household members who have not arrived by the time data collection has been completed. If time allows, a survey team may be able to return to a selected household to complete data collection from eligible members who were absent during the initial visit.

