created when the final selection of households or individuals is made during the sampling process. In cluster surveys, there is a separate form for each cluster, often called a cluster control form, which lists all the households or individuals selected for that cluster. These sample lists and cluster control forms will contain both identifying information and the numeric code described above, and thus can serve as a key to match the code numbers to specific individual participants. This key is necessary to follow-up with specific survey participants if necessary. At the end of the survey, these sample lists will be destroyed or permanently stored separate from the paper data collection forms. Only authorized survey coordinators will have access to the sample lists and data collection forms. Final deposition of all paper and electronic survey materials, including computer datasets and paper forms, will be determined by the organization or agency which funds the survey. In most cases, the sample lists and paper data collection will not return to Atlanta with IERHB personnel.

APPENDIX 1

Nutrition and Health Survey, Afghanistan, 2002

Province	District	Village)	
Cluster number:	_Household number:			
Team code:	Interviewer code:	Date of interview:	/	
			Day	Month

HOUSEHOLD DATA

1)	Does your family now live in your usual place of residence? (circle one)	Yes	/ N o / U nk
	1a) If NO, how long since the family has lived there?	months OR	years
2)	Has anyone in the family received any relief food since the change in government?.	Yes /	No / Unk
3)	What is your main source of water? (circle one)Central piped system /	Truck or water seller	r / Bore hole
	Open W ell / R iver	or stream / Lake or p	ond / Other
4)	Do you use the same source of water now as you did this time last year?	Yes /	No / Unk
5)	How long does it take you to fetch water each time you go to get it?	······	minutes
6)	Results of iodine testing of salt used for last night's food (circle one)I	Positive / Negative	/ Not Done

I would like to ask you about each person who **lived in this household at the time of Eid Qurban 1379** (2001 Gregorian calendar) and children who were born since the time of Eid Qurban:

HOUS Head of on	EHOL house 1 st line	D MEMBI	ERS 1. 2. 3. 4.	Alive (livin Alive (livin Died Missing/L	ng in this ho ng elsewho Jnknown	ousehold) ere)	When was he/she did he/she h feet or leas	became ill, very thin or nave swollen	was she pregnant or at the time of Chil or Nefaz?

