	Per son no.	Age (years)	Sex (circle one)	Curren as of T (circl	nt Status TODAY le one)	If missing or dead, since when? (mm/yy)	Died of which cause? (ask questions)	Walnutrition?	Pregnant or in Chel??
\vdash	1		M / F	1 2	3 4	/		Y / N	Y / N
	2		M / F	1 2	3 4	/		Y / N	Y / N
	3		M / F	1 2	3 4	/		Y / N	Y / N
	4		M / F	1 2	3 4	/		Y / N	Y / N
	5		M / F	1 2	3 4	/		Y / N	Y / N
	6		M / F	1 2	3 4	/		Y / N	Y / N
	7		M / F	1 2	3 4	/		Y / N	Y / N
	8		M / F	1 2	3 4	/		Y / N	Y / N
	9		M / F	1 2	3 4	/		Y / N	Y / N
	10		M / F	1 2	3 4	/		Y / N	Y / N
	11		M / F	1 2	3 4	/		Y / N	Y / N
	12		M / F	1 2	3 4	/		Y / N	Y / N
	13		M / F	1 2	3 4	/		Y / N	Y / N
	14		M / F	1 2	3 4	/		Y / N	Y / N
	15		M / F	1 2	3 4	/		Y / N	Y / N

LIVING WOMEN OF CHILDBEARING AGE (15 – 49 years)

Person no. from table 1 above.	Literate ?	Night blind- ness	Goiter	Preg- nant now?	No. of doses tetanus vaccine	MUAC (cms)	Weight (kgs)	Height (cms)	Hemoglobin (gms)
	Y/N	Y / N	Y / N	Y / N				,,,	
	Y/N	Y / N	Y / N	Y / N				,,	, ,
	Y/N	Y / N	Y / N	Y / N		,	,	,,	, ,
	Y/N	Y / N	Y / N	Y / N		,,	,	,,	,,
	Y/N	Y / N	Y / N	Y / N		,,	,	,,	,,
	Y/N	Y / N	Y / N	Y / N		,	,	,,	,,
	Y/N	Y / N	Y / N	Y / N		,	,	,,	,,
	Y/N	Y / N	Y / N	Y / N		,	,	,,	,,
	Y/N	Y / N	Y / N	Y / N		,	,	,	,
	Y/N	Y / N	Y / N	Y / N					

Clus	ster number:	HH:	_ Child's person number:	Mot	ner's pers	son number:				
Que	stions for adult ca	retaker								
1) F	Relationship of res	pondent to ch	ild:	. Mother	Father	Grandmothe	er Grand	dfathe	r O	ther
2) I	s this child's mothe	er alive?					.Yes	/ N o	/	Unk
3) 5	Sex						M a	le /	Fer	nale
4) [Date of birth OR Ag	ge in months.			/	/	OR _		mo	nths
				[Day Mo	onth Year.				
5) [Does this child hav	e difficulty see	eing at night or in the evenin	g when ot	her peop	ole do not?	Yes	N o	/	Unk
6) 5	Since this time yes	terday, has th	is child breast fed?				Yes /	N o	/	Unk
	6a) If YES, was	breast milk th	is child's main source of foo	d since ye	sterday?		Yes ,	/ N o	/	U nk
	6b) If YES, how	long after birt	h did this child first breastfee	ed?			······		_ h	ours
7) \$	Since this time yes (circle all that are)	terday, has th true) P	is child received anything ot owered milk or infant formul	her than b a / S emi-	reast mil solid or s	lk? solid food / No	Water, one of t	tea, c hese	or ju	ice /
8) \$	Since this time yes	teday, has thi	s child drunk anything from a	a bottle wi	th a nipp	le?	.Yes	/ N o	/	Unk

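### As worded, the example form's only household roster leaves out current residents who joined after Eid Qurban 2001, although eligibility is residence on the survey day

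*Protocol*

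**What the plan says.** Three sections of the protocol define who is to be measured, and they agree. Under Description and source of study population and catchment area, the sample is all members of targeted groups "who reside in those households on the day of data collection". Under Participant inclusion criteria, individuals qualify if, among other conditions, "they live in a selected household at the time of data collection". Under Enrollment procedures, "All household members who fit the criteria for a target group will be included in the survey if consent is received". The Variables list also restricts the child and women's data to those now in the household.

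The roster in Appendix 1 is built on a different rule. It covers each person who "lived in this household at the time of Eid Qurban 1379" (glossed there as 2001) and "children who were born since the time of Eid Qurban". The form is titled as a 2002 survey. Its four status codes are living in this household, living elsewhere, died, and missing or unknown. None of them marks a person who has moved in.

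The measurement forms depend on this roster. The first column of the women's table is "Person no. from table 1 above", and the child form is headed "Child's person number", followed by the mother's number. The Data collection section says that interview questions are read word for word and presents Appendix 1 as an example of such a form.

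**The concern.** A roster tied to a past date is a sensible instrument for the mortality objective (objective 9 under Objectives), because it fixes the group whose deaths are counted. It is not a list of who lives in the household today, yet it is the only list on the form and it supplies the numbers for the prevalence measurements.

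Someone who joined the household after the feast day, and was not born after it, fits neither roster category. Read as written, the form gives that person no line and no number. Joiners may differ in nutritional status from long-standing members, so prevalence could describe the stable part of the household rather than all current residents. The loss could also go unseen. The nonresponse records under Enrollment procedures cover selected households or individuals in the sample, and a person who was never listed need not generate such a record.

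**Working it through.** **Comparing the texts.** No stated figure is in dispute, so the main check sets the two rules side by side.

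| Person | Eligible under the body of the protocol | Listed by the Appendix 1 roster as worded |
|---|---|---|
| Member at the feast day, still there | Yes | Yes |
| Member at the feast day, now elsewhere or dead | No | Yes (for mortality) |
| Child born since the feast day, living there | Yes, if in the target age range | Yes |
| Woman aged 15-49 who joined since | Yes | No |
| Child under 60 months, born before the feast day, who joined since | Yes | No |

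The last two rows are the gap. Nothing in the protocol or the form adds such people: there is no second roster, no status code for joining and no instruction to write them in. The household-member status item in the Variables list has the same four outcomes and no category for joining.

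**Context from the plan's own figures.** The sample size table gives 492 children for wasting at 20%, precision 5 points, design effect 2. With n = DEFF × z² × p(1 − p) / d²:

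2 × 1.96² × 0.20 × 0.80 / 0.05² = 491.7, rounded up to 492. The figure reproduces.

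**Illustrating the bias.** Let f be the share of eligible residents who joined since the reference date, and let D be the prevalence in joiners minus the prevalence in listed residents. Then

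estimate from listed residents − prevalence in all residents = −f × D.

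The documents give neither f nor D. The ranges below are assumptions.

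| f | D = −10 points | D = +10 points | D = +20 points |
|---|---|---|---|
| 2% | +0.2 | −0.2 | −0.4 |
| 5% | +0.5 | −0.5 | −1.0 |
| 10% | +1.0 | −1.0 | −2.0 |
| 20% | +2.0 | −2.0 | −4.0 |

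Entries are percentage points; a minus sign means the survey estimate is too low. For example, with 20% wasting in listed children, f = 10% and D = +20, the value in all residents is 0.90 × 20 + 0.10 × 40 = 22%, and the form returns 20%.

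**Loss of numbers.** If 492 children are eligible and the same shares are unlisted, 482, 467, 443 or 394 remain. The half-width 1.96 × √(2 × 0.16 / n) becomes 5.05, 5.13, 5.27 or 5.59 points. This is minor. The coverage bias matters more, because the confidence interval does not reflect it and a larger sample does not reduce it.

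**The case against.** The strongest reply is that Appendix 1 is only an example, taken from one survey, while the governing text already says that current residents are measured. Households are the sampling unit in that kind of survey, the person number links records rather than selects people, and a sensible team could add a line. The Sampling section describes a recent provincial survey in Afghanistan as having included all members of its target groups.

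Much of this stands. A reader might infer that joiners cannot be selected at all; the documents do not support that, since selection is by household and nothing tells teams to turn an unlisted resident away. Nor does the form show that anyone was missed in an actual survey. A reader might also infer that displaced people in general are missed. They are not: the roster concerns membership of the household, and item 1 of the form asks whether the family is living away from its usual residence, so a family displaced together can still be listed. The gap concerns individuals who joined an existing household.

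What the reply does not remove is the conflict. This is the only form that the protocol offers as a model, its questions are to be read verbatim, and used that way it does not deliver the protocol's own inclusion rule.

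**Conclusion.** The conflict is real and lies in the text: eligibility is current residence, while the only roster feeding the measurement forms is defined by a past date plus births. As worded, the form does not list women, or children born before the reference date, who joined the household later.

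The size and sign of the resulting bias cannot be derived from the documents. Under the assumed inputs it runs from 0.2 points in either direction to 2 points too high or 4 points too low, which is within the 5-point precision planned for wasting. The point concerns the template, and is worth correcting before reuse because missing residents cannot be recovered at analysis.

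Two further inferences about mortality should not be drawn. One is that recording age in years, without birth dates, overstates under-5 person-time by about 11%. That comes from setting 0.8 + 0.2 × 0.5 = 0.90 against 1.00, assuming an even age spread and a recall of about 12 months. It leaves out children who turned five during the recall, who add about 0.2 × 0.5 = 0.10 and bring the total back to 1.00. The other is that infants under 6 months raise doubt at the under-5 boundary; they are plainly under 5.

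**What to change.** Extend the roster to anyone who lived in the household at the reference date, was born since, or lives there today. Add one entry, 'joined since reference date (mm/yy)', left blank for those already present. Take women and children for measurement from the roster lines of people living in the household today. For mortality, use reference-date members plus births, so that the past-date list still does the job it suits. Add one line to the interviewer instructions saying that current residents who joined later are listed and numbered like everyone else.

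The cost is one short column and one line of instruction. A birth month and year for young children would be an optional aid to the mortality calculation; this point does not depend on it.

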Because surveys in emergency-affected populations must be carried out rapidly and are meant to evaluate only those nutritional deficiencies which are 1) most life-threatening, 2) affect the greatest number of persons, and 3) are amenable to immediate intervention, some important nutritional conditions are infrequently evaluated. One example of such a problem is anemia among pregnant women. Although an extremely important problem, achieving a sufficiently large sample of pregnant women in a population-based survey requires the inclusion of too many households to promptly complete an emergency assessment survey. Other assessment methods, such as surveys of antenatal clinic attendees, which are not described in this protocol, may have to be used for such assessment.

Conducting a population-based survey in an emergency-affected population is often a resource-intensive undertaking. Actually reaching remote households often requires the greatest expense and time. For this reason, other objectives may be added to nutrition assessment surveys. Such additions may include assessment of household water supply, source of income, access to health services, health care seeking behaviors, infant feeding practices, and other factors. Nutrition assessment surveys do not usually include the collection of highly sensitive information on sexual behavior, reproduction, or other sensitive topics.

Hypothesis or questions

There are no *a priori* hypotheses in nutrition assessment surveys in emergency-affected populations. The goal of such surveys is to determine the type, prevalence, and severity of nutritional deficiencies in the population in order to design appropriate interventions.

General approach

Nutrition assessment surveys in emergency-affected populations are generally descriptive and intended to provide data on the type, prevalence, and severity of nutritional deficiencies of greatest importance.

PROCEDURES/METHODS

Design

How study design or surveillance system addresses hypotheses and meets objectives

Because the objectives of a nutrition assessment survey in an emergency-affected population are to estimate the prevalence rates of various nutritional conditions, the most appropriate design is that of a cross-sectional survey. No other design will produce a population-based estimate of these outcomes.

Audience and stakeholder participation

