No sub-segment of the population will be specifically excluded from participation in nutrition assessment surveys in emergency-affected populations; however, some population subsegments may not be specifically chosen for inclusion. Women and children are at greater risk of most nutritional deficiencies; therefore, they will be targeted for most nutrition assessment surveys. Men are at substantially lower risk of many nutritional deficiencies and are therefore specifically not targeted for most nutritional assessments. One exception is the assessment of the causes of anemia. Men are often included in such surveys because they are much less susceptible to iron deficiency. Therefore, survey findings indicating that anemia is common among women and children but rare among men provide evidence that iron deficiency is a predominant cause of anemia.

Estimated number of participants

The specific sample size in each nutrition assessment survey depends on many assumptions and factors which may differ from one survey to the next. Commonly, such surveys include 200 - 700 households and all eligible members of target groups who live therein.

Sampling, including sample size and statistical power

The required sample size will be calculated separately for each assessment survey. All sample size calculations use the following assumptions:

- 1) The limit of statistical significance (alpha) = 0.05
- 2) The power (beta) = 0.8

The other assumptions required for sample size calculation will be decided based on the specific population to be assessed. These assumptions include:

- 1) Prevalence of nutritional condition of interest
- 2) Desired precision of point estimate of prevalence, cumulative prevalence, incidence, or mean.
- 3) Population size, if less than 10,000.
- 4) Design effect, if cluster sampling is planned.

The table below shows examples of nutrition conditions of interest, the assumptions used, and the sample size needed which may be used in nutrition assessment surveys in emergency-affected populations. These examples assume a population size greater than 10,000. Of course, the assumptions used and therefore the required sample sizes will differ depending on the nutrition conditions and specific population to be assessed.

Target group and type of malnutrition	Assumed current value	Precision required	DEFF assumed	Sample size needed
Children 6-59 months				
Wasting (< -2 SD)	20%	" 5%	2	492
Stunting (< -2 SD)	50%	" 10%	2	193

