cluster or multi-stage sampling must be done. The primary sampling units differ depending on the organization of the population and the data available. For example, in a recent survey in a province in Afghanistan, a complete list of all villages in the province was available along with approximate population of each village. From this list, 30 villages were selected probability proportional to size as primary sampling units. Upon visiting each of these villages, survey workers, with the assistance of local leaders, constructed a complete list of all households in that village. Households were then selected by simple random sampling, and all members of the target groups of children 6-59 months of age and women of child-bearing age were included in the survey. In large villages, where making a list of all households was not practical, one subsection of the village was chosen at random probability proportional to size. A list of all households in this subsection was then created and sampling of individual households done as described above. The basic sampling unit was the household, which was also the unit of analysis for various household-level variables, such as the source of water and food security. The unit of analysis for most nutrition variables was the individual child or woman.

Regardless of the specific sampling method used, sampling will attempt to achieve equalprobability of selection. That is, each of the basic sampling units in the sampling universe, whether households or individuals, will have the same probability of being included in the survey sample. As a result, data analysis will not require statistical weighting. In order to achieve equal probability sampling, each sampling stage except the last uses probability proportional to size selection. In a hypothetical situation where a survey sample includes 30 clusters of 20 households each, the probabilities of selection at each sampling stage and the final probability of selection for individual households are illustrated below:

Stage 1 Probability of any given PSU* being selected	Proba secc chose	Stage 2 bility of any given ondary unit being en within selected PSU	Stage 3 Probability of any specific HH being chosen within selected secondary unit	Product of individual probabilities = Probability of any specific HH being chosen for survey
30 [°] x No. HHs		No. of HHs in	~	
in PSU .	Х	secondary unit .	$X = 20^{-11} =$	 

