The entire data collection form, including interview questions, is translated into the language or languages spoken by survey team members and survey participants by native speakers of these languages. The translation is then back translated into English by different translators. Differences between the original and back-translated English forms are resolved by the two translators working with the survey supervisor. Interview questions are read verbatim by interviewers during data collection. An example of the English version of such a data collection form is given in Appendix 1.

Interviews. Interviews will be conducted by appropriate survey team members who have received instruction in the type of data to be collected by each specific question and the reason these data are being collected. Interview questions will be read verbatim from the interview form. Interviewees will be allowed to refuse answers to any or all of the questions.

Anthropometric measurements. All anthropometric measurements, most commonly consisting of height, length, weight, and MUAC, will be taken using standard methods. For example, for children 6-59 months of age, all measurements will be taken using the procedures outlined in the UNICEF training manual "How to Weight and Measure Children.." All anthropometric indices will be calculated using either the NCHS/CDC/WHO reference population, or if available, the new WHO reference population. Anthropometric measurements on adults are less standardized. Weight will be measured with a properly calibrated bathroom-type scale. Height will be measured using a portable stadiometer while the subject stands against a vertical surface. For other target groups, including adolescents, methods may differ depending on current knowledge.

Physical examination. In some nutrition assessment surveys, collection of biologic specimens may be infeasible or ill advised. In such cases, survey subjects may be examined for signs or symptoms of specific micronutrient deficiencies. In all cases where protein-energy

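### The example child form asks time to first breastfeeding only of children still breastfeeding, and never asks whether a child was ever breastfed

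*Protocol*

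**What the plan says.** Appendix 1 prints a child form headed as a 2002 Afghanistan survey. Question 6 asks whether the child has breastfed since the same time on the previous day (Yes / No / Unk). Two follow-ups sit beneath it, and each opens with an instruction to ask only after a yes. Question 6a asks whether breast milk was the main food in that day. Question 6b asks how many hours after birth "did this child first breastfee"[d]. No other item on the form asks whether the child was ever breastfed or when breastfeeding began. Age or date of birth is recorded at question 4.

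The section on data collection presents the form as a model: "An example of the English version of such a data collection form is given in Appendix 1". The same section has interviewers read the questions word for word.

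Infant feeding is not among objectives 1 to 9. The Objectives section names it as one of several topics that a survey may add: "access to health services, health care seeking behaviors, infant feeding practices, and other factors".

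On the children covered, the Sampling section says of its Afghanistan example that "all members of the target groups of children 6-59 months of age and women of child-bearing age were included in the survey". The list of variables uses the same age range for the child section.

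**The concern.** Time to first breastfeeding is settled around birth. Breastfeeding in the last day depends on the child's present age and on whether feeding has continued. Filtering the first on the second selects respondents on something that happens after the event being measured.

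Two groups then fall out together at question 6: children who were breastfed and have stopped, and children who were never breastfed. Skipping the second group at a timing question is not wrong in itself, because they have no time to report. The loss is that nothing identifies them, so they can be neither counted in a denominator nor deliberately left out of one. Analysis cannot repair this, because the answers were never collected.

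At stake is whether a survey that adds infant feeding and takes this form as its model could report initiation for the child population, or only for children still breastfeeding on the survey day.

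**Working it through.** The protocol states no figure for breastfeeding initiation, so there is none to reproduce. The check has three parts.

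**1. Who reaches question 6b**

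| Child | Question 6 | Question 6b | What the data show |
|---|---|---|---|
| Still breastfeeding | Yes | Asked | Initiation time |
| Breastfed, now weaned | No | Skipped | Nothing |
| Never breastfed | No | Skipped | Nothing |

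The last two rows are identical in the data. An Unk at question 6 also leads to a skip. The form does not say whether the condition on 6b refers to question 6 or to 6a. If it refers to 6a, the group asked is smaller still.

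**2. Share asked**

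Inputs: ages 6-59 months, which is 54 one-month bands (Sampling section and list of variables). Assumptions: uniform ages, and a single breastfeeding duration *d* in months. The document gives no duration, so a range is shown.

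Share asked = (*d* − 6) / 54

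| *d* (months) | Calculation | Share asked |
|---|---|---|
| 12 | 6/54 | 11% |
| 18 | 12/54 | 22% |
| 24 | 18/54 | 33% |
| 30 | 24/54 | 44% |
| 33 | 27/54 | 50% |
| 36 | 30/54 | 56% |

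The share depends on the age band reported. For children aged 6 to under 24 months it is (*d* − 6) / 18: 33% at 12 months, 67% at 18 months and 100% at 24 months.

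**3. Precision, for scale only**

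Inputs: the protocol's example of 492 children with design effect 2 (wasting row of the sample size table), and 95% confidence limits. That row reproduces: 2 × 1.96² × 0.20 × 0.80 / 0.05² rounds up to 492. The number was not chosen for a feeding item.

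Half-width for a proportion of 50% = 1.96 × √(2 × 0.25 / *n*), with *n* = 492 × share asked.

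| *d* (months) | Children asked | Half-width (percentage points) |
|---|---|---|
| 12 | 55 | 18.7 |
| 18 | 109 | 13.3 |
| 24 | 164 | 10.8 |
| 30 | 219 | 9.4 |
| 36 | 273 | 8.4 |
| All 492 asked | 492 | 6.2 |

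If the item is reported only for a young age band, the fix does not bring the half-width to 6.2. With a band of 6 to under 24 months, at most 492 × 18/54 = 164 children would answer.

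**The case against.** The strongest reply is that the protocol fixes nothing here. The form is an example from one survey, and questions are pretested and revised during training. Infant feeding is an optional topic, and no initiation indicator or denominator is defined anywhere. All of that stands and keeps the point small. It does not remove it: the form is the model offered to later surveys, and a skip printed on it will be followed as printed.

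A second reply is that limiting the question to children still breastfeeding shortens recall, which matters when the respondent may be a father or grandparent (question 1). The protocol does not give this reason. An age limit based on question 4 would serve the same purpose without dropping weaned children inside the band. It is fair to concede that if every ever-breastfed child continued to 24 months and reporting stopped there, the present skip would reach the same ever-breastfed children. The gain would then be only that never-breastfed children are identified.

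Two stronger readings are tempting. A reader might infer that the form always covers a minority of children. That depends on duration: under the assumptions above the share reaches 50% at 33 months and 56% at 36 months. A reader might also infer that the survey overstates early initiation by a calculable amount. For example, one could assume early initiation in 50% of children still breastfeeding and 30% of the rest. At *d* = 24 the all-children figure would be 0.333 × 50% + 0.667 × 30% = 37%, against 50% from the form. The document supports neither the contrast nor its direction. The model also has every child stop at the same age, so stopping cannot depend on when feeding began, and any contrast would be one between age groups. If the groups do not differ, only precision and the count of never-breastfed children are lost.

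**Conclusion.** The defect in the skip is plain from the form and needs no assumption: a past event is asked about only after a yes to current breastfeeding, and weaned children cannot be told from never-breastfed ones. A survey that adds infant feeding and uses this form could not report initiation for all children in an age band where some have stopped or never started.

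The share asked, about 11% to 56% for durations of 12 to 36 months, rests on uniform ages over 6-59 months and on a duration that the document does not supply. Bias is conditional on a difference in initiation between children still breastfeeding and those who have stopped, and its size cannot be derived. No listed objective or sample size in the protocol depends on this item. It is a cheap improvement to an example form.

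**What to change.** - Put *Was this child ever breastfed? Yes / No / Unk* before question 6.
- Make the timing question depend on that new item and not on question 6 or 6a. Leave 6a under question 6.
- Ask and report initiation time for a stated age band, using the age at question 4.
- Report the number never breastfed, and state whether the denominator is all children in the band or only those ever breastfed.

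The cost is one extra item and a few seconds per child. Including weaned children adds some recall error, which the age band limits. Sample sizes and objectives 1 to 9 are unaffected.
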